Given the median duration of viremia is 14-20 days in mild cases, we will assume the null hypothesis that in the placebo cohort the median time to release from quarantine is 10 days from receiving a positive test. In order for HCQ to be considered more effective in this treatment setting we aim to see a median time to release from quarantine of 5 days. These values correspond to daily hazard rates of 0.069 and 0.139 respectively. We will randomize 1:1 HCQ to control and with 100 patients with 50 in the placebo arm and 50 in the HCQ arm. The one-sided z- test (alpha=.05) will have an overall 95% power to detect a significant difference between the two groups with medians of 10 and 5 days.

Based on the new CDC guidelines for quarantine release we will modify the analysis as follows: Given the median duration of viremia is 14-28 days in mild cases, we will assume the null hypothesis that in the placebo cohort the median time to release from quarantine is 14 days from receiving a positive test. In order for HCQ to be considered more effective in this treatment setting we aim to see a median time to release from quarantine of 7 days. These values correspond to daily hazard rates of 0.048 and 0.094 respectively. We will randomize 1:1 HCQ to control and with 100 patients with 50 in the placebo arm and 50 in the HCQ arm. The one-sided z- test (alpha=.05) will have an overall 93% power to detect a significant difference between the two groups with medians of 14 and 7 days.

The *hypothesis* will be tested using a one-sided test, with a z-score corresponds to the log of the hazard-ratio for recovery between the two groups. We will obtain estimates of the hazard ratio and group median survival, and 95% CI, from Cox regression. As a secondary analysis, we will stratify the analysis, and obtain separate estimates of the hazard-ratio by group. However, we are not powered to test the interaction for significance, and we do not expect significance within group.

Given that 20 subjects were recruited and treated under the old CDC guidance, we will conduct a primary analysis based on the updated 10-days from onset criterion. For the subjects who were released under the old criterion, this number will be constructed by assessing when a patient would have been released under the new rules. We will follow that with additional secondary analyses to assess the sensitivity of the results to the change in

The PATCH Trial

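### The amended Sub-Study 1 design prints daily release probabilities (0.048, 0.094) as hazard rates; medians of 14 and 7 days give 0.0495 and 0.0990, and the 93% power should be recomputed from stated inputs

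*Protocol*

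**What the plan says.** Protocol section 13.1, Sub-Study 1, gives two designs one after the other.

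- **Original design**, medians of 10 and 5 days: "These values correspond to daily hazard rates of 0.069 and 0.139 respectively". The test "will have an overall 95% power to detect a significant difference between the two groups with medians of 10 and 5 days".
- **Amended design**, after the CDC guidance changed. The null is that "in the placebo cohort the median time to release from quarantine is 14 days from receiving a positive test"; for HCQ, "we aim to see a median time to release from quarantine of 7 days". Then: "These values correspond to daily hazard rates of 0.048 and 0.094 respectively". The size is unchanged, "100 patients with 50 in the placebo arm and 50 in the HCQ arm", and the one-sided 5% test "will have an overall 93% power to detect a significant difference".

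The interim analysis paragraph for Sub-Study 1 repeats 93% for 7 versus 14 days. The boundary table below it has a total time of 60, a maximum information of 2000.1128 and a final efficacy boundary of 1.6808 in absolute value. The test is described as a z-score for the log hazard ratio, with estimates from Cox regression. No accrual period is given for either design. The SAP covers Sub-Study 3 only and does not return to this.

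**The concern.** Halving an exponential median doubles the hazard. The original pair does this (0.139/0.069 is 2.0 within rounding). The amended pair does not: 0.094/0.048 = 1.958. Rounding cannot explain it, because the correct values would print as 0.050 and 0.099.

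These are the stated inputs to the power of the primary test in a sub-study that the protocol's introduction says was still enrolling. Anyone who re-plans from the printed hazards would work with medians of 14.4 and 7.4 days and not the stated 14 and 7. It also leaves open whether the 93% was calculated from the medians or from the mislabelled rates.

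**Working it through.** **1. Converting the medians.** Hazard = ln2/median; probability of release per day = 1 − 2^(−1/median).

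| Median (days) | Hazard | Daily probability | Printed |
|---|---|---|---|
| 10 | 0.0693 | 0.0670 | 0.069 |
| 5 | 0.1386 | 0.1294 | 0.139 |
| 14 | 0.0495 | 0.0483 | 0.048 |
| 7 | 0.0990 | 0.0943 | 0.094 |

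The original pair matches the hazard column and the amended pair matches the probability column. The printed amended rates are low by 3% (0.048 against 0.0495) and 5% (0.094 against 0.0990). Read as hazards they imply medians of ln2/0.048 = 14.4 and ln2/0.094 = 7.4 days.

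**2. Inferring a schedule.** Accrual is not stated, so this step is an assumption. Take 50 per arm, exponential times, uniform accrual over A days and analysis at T = 60 days. The chance that a participant has the event is 1 − [e^(−h(T−A)) − e^(−hT)]/(hA). For the original hazards, the information on the hazard difference is 1/(h₁²/d₁ + h₂²/d₂), where d₁ and d₂ are expected events. It equals the printed 2000.1128 at A = 45.0 days.

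**3. Reproducing the stated powers at A = 45.** Power ≈ Φ(ln HR × √(D/4) − 1.6808), with D the total events.

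- Original, 10 v 5: D = 44.6 + 49.0 = 93.6; 0.693 × √23.4 − 1.6808 = 1.672; power 95.3% (stated 95%).
- Amended, printed rates: D = 40.0 + 47.2 = 87.2; 0.672 × √21.8 − 1.6808 = 1.457; power 92.7% (stated 93%).
- Amended, correct hazards: D = 40.5 + 47.5 = 88.0; 0.693 × √22.0 − 1.6808 = 1.570; power 94.2%.

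A group-sequential calculation with the printed boundaries and information fractions gives 95.1%, 92.6% and 94.0%. Log-rank simulation at the final boundary gives 95.6%, 92.8% and 94.3%.

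**4. Sensitivity to the unstated accrual** (formula of step 3, T = 60).

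| Accrual (days) | Printed rates | Correct hazards |
|---|---|---|
| 30 | 94.0% | 95.2% |
| 45 | 92.7% | 94.2% |
| 53 | 91.3% | 93.0% |
| 60 | 89.0% | 90.9% |

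The gap is 1 to 2 points throughout, always with the correct hazards higher. The correct hazards also give 93%, at about 53 days' accrual.

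**5. A check on the reconstruction.** The protocol states a 30% chance of stopping for efficacy at the first look under 14 v 7. At A = 45, with information fraction 0.366 and boundary 2.7370, the printed rates give Φ(3.138 × √0.366 − 2.7370) = 20%, and the correct hazards Φ(3.250 × √0.366 − 2.7370) = 22%. Neither reaches 30%.

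**The case against.** The strongest reply concerns the power. A reader might infer from step 3 that the 93% is wrong and should read 94%. The documents do not support that, for these reasons:

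- The 45 days comes from an information figure that is identical in the original protocol's 10 v 5 table, so it describes a different design from the one in question.
- Correct hazards with about 53 days' accrual also give 93%. So does the Freedman form at 45 days: √88.0 × (1/3) − 1.645 = 1.48, or 93.1%.
- The inference uses information on the hazard difference, as the boundary table does, but computes power on the log hazard ratio, as the text does. Kept on the difference scale, (h₂ − h₁) × √information − 1.6808 gives 92.2% for the original design (0.0693 × √2000), 89.6% for the printed rates (0.046 × √4083) and 91.1% for the correct ones (0.0495 × √3745). None matches its stated figure.
- The first-look chance of 30% is not reproduced, so the amended run used settings that the reader cannot see.

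All of this stands. Two further replies have partial force. Release is judged daily, and in discrete time a daily hazard is a probability. But the original paragraph uses the same label for continuous hazards, and the planned Cox analysis works on that scale, so the two paragraphs still conflict. It is also said that nothing downstream depends on the rates. That is right for the efficacy boundaries, which depend on alpha and the information fraction, and the protocol's conditional-power rule applies to Sub-Study 3 only. It does not make the printed inputs correct.

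**Conclusion.** The labelling error is certain and can be checked by hand: 0.048 and 0.094 are daily release probabilities, and the hazards for medians of 14 and 7 days are 0.0495 and 0.0990, with ratio 2.00.

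The effect on power is conditional. If the 45-day accrual implied by the original design's information figure also applies to the amended one, with exponential times and uniform accrual, then the 93% matches the mislabelled rates and the corrected power is about 94%. That would be an understatement of about 1.5 points, in the conservative direction, and 100 patients would remain enough. Since the amended accrual is not stated, this is possible but not shown. The point is minor: it changes neither the sample size nor an efficacy boundary.

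**What to change.** In Protocol section 13.1, amended Sub-Study 1 paragraph, replace the two rates with 0.0495 and 0.0990 and add the hazard ratio, 2.00. State the accrual period and follow-up assumed. The sponsor should then recompute the 93% from those inputs, both there and in the interim analysis paragraph, and check the early-stopping chances given beside it in the same run. The figure should come from the sponsor's own schedule; 94% should not be inserted on the strength of an inferred one.

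The cost is two numbers, one sentence and a re-run of the power calculation. Sample size, test, efficacy boundaries and conduct are untouched.

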3.1.2 Competent and capable to sign informed consent

3.1.3 Subjects meeting the following criteria by arm:

3.1.3 Sub-Study 1:

- Age ≥40 years since the risk of prolonged disease that progresses to severe COVID-19 disease increases with age.
- PCR-positive for the SARS-CoV2 virus
- Fever or cough or shortness of breath
- ≤4 days since the first symptoms of COVID-19 and date of testing
- Not requiring hospitalization and is sent home for quarantine.
- Not taking azithromycin at the time of enrollment
- Symptomatic at the time of enrollment
- Must live within 30 miles of HUP or Penn Presbyterian Medical Center to facilitate drop-off of medication
- Must have access to a working computer, or smartphone and have internet access
- Must be willing to fill out a daily symptom diary
- Must be available for a daily phone call,
- Must take their own temperature twice a day
- Must be willing to report the observed symptoms and development of COVID-19 in the co-inhabitants of the residence at which the quarantine will be served.

Sub-Study 3 Health Care Worker Prevention

- Healthcare worker at HUP or PPMC (Healthcare worker is defined as: a UPHS employee that physically interact with COVID-19 patients e.g., doctors, nurses, respiratory techs, certified nursing assistants, emergency room techs, OB ultrasound techs).
- ≥20 hours per week of clinical work scheduled in the coming 2 months during the COVID-19 pandemic
- No fever, cough, or shortness of breath in the past 2 weeks unless a SARS-CoV-2 test was performed for these symptoms and the result was negative prior to enrollment

The PATCH Trial

- 3.1.4 Sub-studies 1 and 3: Willing to report compliance with HCQ in the form of a diary
- 3.1.5 Sub-Studies 1 and 3: Participants are willing to collect oral fluid using a simple applicator that is provided, and freeze these samples.
- 3.1.6 Not pregnant and/or breastfeeding, as determined below:
Sub-Study 1 and 3: Not known to be pregnant or breast feeding as determined through self-report

[All participants] 3.1.7 Patients must be able to swallow and retain oral medication and must not have any clinically significant gastrointestinal abnormalities that may alter absorption such as, but not limited to malabsorption syndrome, major resection of the stomach or bowels, gastric bypass, lap banding.

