10.2 Response Criteria

Sub-Study 1: Time to release from quarantine. The criterion is afebrile for 72 hours AND improvement of symptoms AND at least 7 or 10 days have passed since symptoms started (according to contemporary CDC guidelines). To quantitatively assess improvement of symptoms the grading system in Section 8.5 will be used.

The PATCH Trial

May 2020. There was a change in CDC guidelines on quarantine time following onset of symptoms, changing from 7 to 10 days. We have adopted the new guidelines, but some of the earlier patients enrolled in the study were released in a shorter time than they would have been under the new guidelines. Because the response is time to release, we will record both release dates for each patient. While the release based on 10 days will be the primary outcome, we will run a parallel analysis of the 7-day measure as part of a sensitivity analysis.

Sub-Study 3: Measurement of SARS-CoV-2 positivity defined by PCR. Time to infection will be defined as the time in days from enrollment on the study to time to COVID-19 symptoms.

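### Sub-Study 1's primary Cox analysis names no baseline covariate; adding age and days from symptom onset to test would be a low-cost efficiency gain, not the correction of an error.

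*Protocol*

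**What the plan says.** Protocol section 13.1 describes the SS1 primary test as one-sided, "with a z-score corresponds to the log of the hazard-ratio for recovery between the two groups", and then adds: "We will obtain estimates of the hazard ratio and group median survival, and 95% CI, from Cox regression". No covariate or stratification factor is attached to either statement. The design claim under the 10-day release rule is: "The one-sided z- test (alpha=.05) will have an overall 93% power". It applies to assumed medians of 14 days on placebo against 7 on HCQ. On the hazards the section states: "These values correspond to daily hazard rates of 0.048 and 0.094 respectively".

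Stratified analyses appear twice in 13.1, both times as secondary. The first does not name its factors; the second serves as a sensitivity check on the change in CDC release rules. Section 5.0 names no stratification factor for SS1 randomization.

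Two baseline variables are already in hand:

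- **Age.** Section 3.1.3 justifies the lower age limit of 40 "since the risk of prolonged disease that progresses to severe COVID-19 disease increases with age", and month and year of birth are recorded at registration.
- **Onset-to-test days.** Eligibility allows at most 4 days from first symptoms to the test. The endpoint clock starts at the positive swab (13.1), while release requires that "at least 7 or 10 days have passed since symptoms started" (10.2), with the 10-day version primary.

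**The concern.** With 50 patients per arm, baseline prognosis can differ between arms by chance, and variation in prognosis that the model ignores works against a Cox comparison. The protocol itself points to age. The onset date also enters the release criterion directly: on a clock that starts at the swab, the earliest possible release runs from day 10 − 4 = 6 to day 10 − 0 = 10, and each patient's value is fixed before randomization. If such variables predict release, an arm-only model gives up power that could be had from data already collected. Because nothing is prespecified, a later adjusted analysis would also be open to the charge that its covariates were picked after the data were seen.

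**Working it through.** **1. Reproduce the stated power.** Inputs from 13.1: hazards 0.048 and 0.094, 50 per arm, one-sided 0.05, total time 60 days. Accrual over 45 of the 60 days is inferred, because it reproduces the information fractions (0.366, 0.674) and maximum information (2000.1) that 13.1 prints and that match its 10 v 5 day calculation.

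- Hazard ratio = 0.094/0.048 = 1.958 (ln2/14 and ln2/7 would give exactly 2.0).
- Event probability for hazard h = 1 − (e^(−15h) − e^(−60h))/(45h). This gives 0.801 and 0.943, so expected events = 50 × 0.801 + 50 × 0.943 = 87.2.
- Fixed-design power = Φ(√(87/4) × ln 1.958 − 1.645) = Φ(3.134 − 1.645) = Φ(1.49) = 93.2%.
- With the printed efficacy boundaries 2.7370, 2.2814 and 1.6808: 93.0%.

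The stated 93% is therefore the power of the comparison without covariates.

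**2. Add prognostic spread.** The documents give no covariate effects, so the following is assumed. Let s be the standard deviation of log hazard explained by the baseline covariates. Simulation: 100 patients, three normal covariates, the accrual above, 6000 runs per row, final look only at z = 1.645. Two readings of the planned hazard ratio are shown, because 13.1 does not say which is meant. Entries are power in %.

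| s (assumed) | Conditional HR 1.958: arm only | adjusted | Marginal HR about 1.96: arm only | adjusted |
|---|---|---|---|---|
| 0 | 92.6 | 92.3 | – | – |
| 0.2 | 91.1 | 91.4 | 92.6 | 93.1 |
| 0.3 | 89.6 | 91.8 | 92.9 | 94.3 |
| 0.5 | 86.0 | 92.4 | 92.8 | 97.2 |
| 0.7 | 78.6 | 90.8 | 92.4 | 98.6 |
| 1.0 | 65.8 | 90.3 | 92.5 | 99.8 |

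The change is −0.3 points at s = 0, up to 2.2 at s = 0.3, and 4.4 (marginal) to 6.4 (conditional) at s = 0.5. Simulated one-sided type I error, with one covariate, was 4.8 to 5.7% across the two analyses. In the conditional columns the mean arm-only hazard ratio falls from 1.97 (s = 0) to 1.91 (0.3) and 1.81 (0.5), against about 2.0 adjusted.

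**3. Onset-to-test days alone.** Assume 0 to 4 days, uniform, with release impossible before day 10 from onset. If onset day acts only through that floor, linear adjustment moves power from 92.2 to 92.5%. If it also shifts recovery by an assumed 0.2 in log hazard per day, power moves from 89.6 to 94.1%. In a separate run of 2000 with the floor, stratifying by onset day reduced power from 0.93 to 0.87, while a linear term gave 0.94.

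**4. Chance imbalance.** The SD of the between-arm difference in a standardized prognostic score is √(2/50) = 0.2. At s = 0.3 to 0.5 this is 0.06 to 0.10 on the log hazard ratio, or 9 to 14% of ln 2 = 0.693.

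**The case against.** The strongest reply is that nothing here is wrong. The sample size rests on group medians, a marginal contrast, and the arm-only test delivers the stated power for that contrast. On the marginal reading it stays at about 92 to 93% whatever the covariates do. It needs no covariate model at the first look, when events are few, and it matches the power calculation. All of this stands, so the point is about efficiency only.

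Particular objections also stand in part:

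- The age sentence is an eligibility rationale about progression to severe illness. It does not say that age predicts time to release, and entry is already limited to 40 and over. Age is a plausible predictor, not a demonstrated one.
- Onset day adds almost nothing if it works only through the release floor, and a hard floor fits a proportional-hazards term imperfectly.
- A separate SS1 analysis plan may exist; none is among these documents.

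A reader might infer that a symptom score is also available for adjustment. The documents do not support that. Table 4 schedules the score daily during treatment and leaves the pre-treatment cell empty. A baseline value is only implied by the progression guideline in 10.3. The symptom list also differs between the original protocol, which scores fever, and the current one, which has abdominal pain in its place.

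A reader might also infer that the arm-only hazard ratio is biased toward 1. The hazard ratio is non-collapsible: the arm-only and covariate-adjusted values answer different questions, and one being nearer 1 is not bias.

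**Conclusion.** This is a worthwhile efficiency improvement to a valid analysis. Its size depends on covariate strength that the documents do not give: about 0 to 2 points of power at an assumed SD of log hazard of 0.3 or less, about 4 to 6 points at 0.5, and no material loss if the covariates are not prognostic. The larger losses at s = 0.7 and 1.0 arise only when the planned hazard ratio is read as conditional and the covariates are strong; nothing in the documents establishes either. It would therefore be wrong to conclude that SS1 is underpowered as planned, or that the arm-only analysis has no merit. The recommendation rests on small cost and a possible gain. The planned secondary stratified analyses do not meet it, because their factors are unnamed or tied to the CDC change.

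**What to change.** In section 13.1, before any further unblinded SS1 comparison, prespecify the primary model as Cox regression with arm, age (continuous) and days from symptom onset to test (linear, not as strata). The documents do not show whether an SS1 interim analysis has already taken place. Keep the one-sided z and the Hwang-Shih-DeCani spending rule, with boundaries set from actual information at each look, as 13.1 already provides. State that the hazard ratio is conditional, report the arm-only hazard ratio alongside, and name the factors for the secondary stratified analysis. Do not include a symptom score unless a pre-treatment score is actually recorded, and never adjust for scores taken on treatment.

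The cost is a few sentences and no new data. The estimand becomes a conditional hazard ratio, which differs from the marginal contrast behind the power calculation. Group medians should still come from an arm-only summary, since medians from the adjusted model depend on covariate values. The onset-day term may fit proportional hazards imperfectly because of the release floor.

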Sub-Study 3, prophylaxis in hospital workers: The transmission of SARS-COV2 from patient to hospital worker depends on many factors including specifics of standard care to prevent transmission, but especially on the number of patients seen at a given hospital or outpatient practice. Across China the reported hospital worker infection rate is 3.8%, but in Wuhan it is reported as 58% at the height of the epidemic. We will use a

10% transmission rate as the null hypothesis (low dose group). In order for HCQ to be considered effective our alternative hypothesis will be a 1% transmission rate. With a 1:1 randomization for the HCQ to control arms we would require a total of 200 hospital worker subjects total for Arm 4. With the placebo group of 100 subjects and the h HCQ arm of 100 subjects, a one-sided z-test ($\alpha=0.05$) comparing the rates in the two groups would have an 80% power to detect a significant difference when the difference in the population rates

The *PATCH Trial* is at least 9%.

The *hypothesis* will be tested using a one-sided test, with a z-score corresponds to the log of the odds-ratio for recovery between the two groups. We will obtain the estimate of the odds ratio, and 95% CI, from logistic regression.

Interim analysis: We will perform two interim analyses at 25% and 50% completion of participant enrollment, testing for early efficacy or futility, using z-score boundaries that follow Hwang-Shih-DeCani alpha spending rules. Following those rules, we have 84% power using 100% of the sample, if our under our 10% versus 1% scenario is true. Under those circumstances, we have a 6% chance of stopping for early efficacy at the first interim analysis. We also have an 81% chance of stopping early for efficacy at the first interim analysis if the low dose arm really has 45% infection instead of 10%. Under normal circumstances (10% v 1%), we have a 27% chance of stopping for early efficacy at the second interim analysis. We also have an 80% chance of stopping early for efficacy at the second interim analysis if the low dose arm really has 23% infection instead of 10%.

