4	May 24, 2020	None	None
5	June 23, 2020	1. DSMB charter 2. Clarification that PCR+ positive patients at baseline are not evaluable for primary endpoint 3. secondary objective of # shifts missed is removed 4. clarification that subjects that discontinue study medication can still complete study procedures	1. Independent DSMB recommends early termination or continued accrual 2. Evaluable patients for primary outcome finalized

Study Objectives

PRIMARY OBJECTIVES

Rate of COVID-19 infection (cumulative incidence) during eight weeks of treatment or followup, as determined by NP swab testing performed by study staff at the 4-week and 8-week timepoints OR confirmed positive NP swab testing via a CLIA-approved clinical test performed before the 8-week timepoint.

SECONDARY OBJECTIVES

Rate of treatment related adverse events, as patient-reported outcomes obtained during weekly telephone calls to all subjects, following the Common terminology criteria for adverse events version 5.0 (CTCAE v 5.0).

CORRELATIVE OBJECTIVE

To bank serially collected samples to enable correlative science related this trial

Statistical Hypotheses

We hypothesize that there will be a statistically significant fewer new SARS-CoV-2 positive cases in the HCQ-treated cohort compared to the placebo-treated cohort during the 8 weeks of follow up.

Sample size and statistical treatment

The transmission of SARS-CoV2 from patient to hospital worker depends on many factors including specifics of standard care to prevent transmission, but especially on the number of patients seen at a given hospital or outpatient practice. Across China the reported hospital worker infection rate is 3.8%, but in Wuhan it is reported as 58% at the height of the epidemic. We will use a 10% cumulative incidence as the null hypothesis. In order for HCQ to be considered effective our alternative hypothesis will be a 1% transmission rate. With a 1:1 randomization for the HCQ to control arms we would require a total of 200 hospital worker subjects total. With the placebo group of 100 subjects and the HCQ arm of 100 subjects, a one-sided z-test ($\alpha=0.05$) comparing the rates in the two groups would have 84% power to detect a significant difference when the difference in the population rates is at least 9%. The design is akin to a randomized phase II design and not a randomized phase III design.

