The hypothesis will be tested using a one-sided test, with a z-score corresponds to the log of the odds-ratio for remaining uninfected between the two groups. We will obtain the estimate of the odds ratio, and 95% CI, from logistic regression.

Randomization process

The study is a randomized, double-blind controlled trial. Randomization will be conducted via the Penn Investigational Drug Service, following a block randomization strategy. Fixed blocks of 8 will be assigned using well-established proprietary software for clinical trials (Sealed Envelope, London UK). Randomization will be kept confidential at the IDS until the pre-specified interim and final analyses. If any SAEs occur or if subjects become SARS-CoV-2 positive, those subjects can be unblinded by written request of the PIs to the IDS team.

General

Statistical analyses will be performed using Stata v16, SAS ® software v9.4 or later, or R. All statistical analyses will mirror those of the treatment groups of Hydroxychloroquine (HCQ) and Placebo.

Without any other specification, all statistical tests will be conducted with a two-sided 5% error. The primary hypothesis will also be tested with a 5% type-one error, but that error will be one sided, corresponding to the nature of the interim analyses. Small portions of the type 1 and type 2 error will be spent on interim

analyses, following Hwang-Shih-DeCani alpha and beta spending rules, leaving error rates at the final analysis slightly reduced.

Prior to analysis, data will be screened, cleaned, and examined for outliers using standard methods. Demographic and outcome variables will be summarized overall and by treatment. Continuous measurements will be described by means \pm standard deviations or medians with minimum and maximum or the interquartile range (IQR). Binary outcomes will be described by frequencies and proportions (percentages).

The results of randomization will be examined by comparing treatment arms for demographic and other relevant variables, to test for incidental bias. We will use two-sample statistics (t-tests or Wilcoxon tests) or contingency table methods (chi-square or Fisher's exact tests) as appropriate.

Primary Analysis

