The primary analysis will consist of a z-test, corresponding to the log of the odds-ratio for the proportion well in the HCQ group, versus the proportion well in the placebo group at the end of 8 weeks. The estimate will be made using either logistic regression or directly using contingency table methods. Tests will be one-sided, with type one error based on the alpha spending plan, with an overall type one error of 5%.

Interim Analysis

We will perform two interim analyses at 25% and 50% completion, testing for early efficacy or futility, using z-score boundaries that follow Hwang-Shih-DeCani alpha and beta spending rules (Z-value boundaries are shown in the table below).^{1,2} Following those rules, we have 84% power using 100% of the sample, if our infection rate in placebo compared to hydroxychloroquine is 10% versus 1% scenario is true. Under those circumstances, we have a 6% chance of stopping for early efficacy at the first interim analysis. Under normal circumstances (10% vs 1%), we have a 27% chance of stopping for early efficacy at the second interim analysis. We also have an 80% chance of stopping early for efficacy at the second interim analysis if the low dose arm really has 23% infection instead of 10%. Results of the interim analysis will be presented to the Data Safety and Monitoring Board (DSMB) by the study team. The DSMB will provide a recommendation of continuing or terminating the study early.

Z-Value Boundaries			
	Boundaries		Information
Stage	Efficacy	Futility	Proportion
1	2.9473	-1.2318	0.2500
2	2.5825	-0.2676	0.5000
3	1.6664	1.6664	1.0000

P-Value Boundaries			
	Boundaries		Information
Stage	Efficacy	Futility	Proportion
1	0.00160	0.89099	0.2500
2	0.00491	0.60550	0.5000
3	0.04782	0.04782	1.0000

References

- 1- Hwang, I. K., Shih, W. J., and De Cani, J. S. (1990). Group sequential designs using a family of Type I error probability spending functions. *Statistics in Medicine* 9, 1439– 45.
- 2- Jennison, C. and Turnbull, B. W. (2000). *Group Sequential Methods with Applications to Clinical Trials*. Chapman and Hall/CRC, Boca Raton, FL.

Final analyses

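### Protocol Section 13.1 gives Sub-Study 3 two powers (80% and 84%) for one design, and its 6% first-look stopping chance fails at 25 per arm

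*Protocol*

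**What the plan says.** Protocol Section 13.1 (Sub-Study 3) assumes infection rates of 10% on placebo and 1% on HCQ, with 100 per arm and a one-sided z-test at 0.05. The sample-size sentence says this "would have an 80% power to detect a significant difference when the difference in the population rates" reaches 9 points. The interim paragraph says of the same scenario that "we have 84% power using 100% of the sample".

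The SAP (Sample size and statistical treatment) says the design "would have 84% power to detect a significant difference when the difference in the population rates is at least 9" percent, and its Interim Analysis section repeats 84%. The 80% does not appear there as a power.

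The Protocol's test is one-sided, "with a z-score corresponds to the log of the odds-ratio for recovery between the two groups". The SAP has "with a z-score corresponds to the log of the odds-ratio for remaining uninfected between the two groups" and adds under Primary Analysis: "The estimate will be made using either logistic regression or directly using contingency table methods". Neither document gives the form of the z or a rule for an arm with no infections.

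On early stopping at 10% v 1%, both documents state that "we have a 6% chance of stopping for early efficacy at the first interim analysis" and give 27% for the second look. Both also give 80% for the second look at a 23% placebo rate. The Protocol alone adds "We also have an 81% chance of stopping early for efficacy at the first interim analysis", for a 45% placebo rate.

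**The concern.** Two powers are printed for one set of inputs, and a reader cannot tell which belongs to the planned test. The 9-point wording can also be read as covering any 9-point benefit. Someone interpreting a null result could then believe that such a benefit had been ruled out with 80% or 84% power, whatever the background infection rate. That rate was uncertain: Section 13.1 itself cites 3.8% to 58% and explores 23% and 45%.

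The DSMB, meanwhile, is told to expect a 6% chance of an efficacy stop at a look with about 25 people per arm and 2.5 expected placebo infections. A normal approximation is doubtful there.

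**Working it through.** **Inputs.** Rates of 10% and 1%, n = 100 per arm and one-sided 0.05 come from Protocol 13.1. Looks after 50 and 100 of 200 evaluable participants come from the DSMB charter and SAP; I take these as 25 and 50 per arm. Efficacy bounds of 2.9473, 2.5825 and 1.6664 at information 0.25, 0.5 and 1 are printed in both documents.

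**1. Reproducing the stated figures.** The pooled normal formula, with p̄ = 0.055, is

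Φ{[(p1 − p2)√n − z√(2p̄(1 − p̄))] / √(p1(1 − p1) + p2(1 − p2))}.

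For 10% v 1%, √(2 × 0.055 × 0.945) = 0.3224 and √(0.0900 + 0.0099) = 0.3161.

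- Final, n = 100, z = 1.645: (0.900 − 0.530)/0.3161 = 1.17, power 87.9%.
- The same with a continuity correction of 1/n: (0.800 − 0.530)/0.3161 = 0.853, power 80.3%.
- Look 1, n = 25, z = 2.9473: (0.450 − 0.950)/0.3161 = −1.58, chance 5.7% (stated 6%).
- Look 2, n = 50, z = 2.5825: (0.636 − 0.833)/0.3161 = −0.62, chance 26.7% (stated 27%).
- Look 1 at 45% v 1%: 81.0% (stated 81%). Look 2 at 23% v 1%: 80.3% (stated 80%).

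One formula therefore gives all four stopping chances, but it gives 87.9% for power, which is neither stated figure. The 80% agrees with the continuity-corrected formula. The 84% is close to an exact Fisher test at the printed p-value bounds (84.8%).

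**2. Can the looks turn 80% into 84%?** No. A drift of 2.487 gives 80% with no looks. With the printed bounds (trivariate normal), the same drift gives 79.6%.

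**3. Exact results.** These come from enumerating binomial counts at 25, 50 and 100 per arm, with efficacy bounds only. Entries are percentages.

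| Statistic | Look 1, 10 v 1 (stated 6) | By look 2, 10 v 1 (27) | Look 1, 45 v 1 (81) | By look 2, 23 v 1 (80) | Power, 10 v 1 |
|---|---|---|---|---|---|
| Pooled z | 0.2 | 16 | 89 | 89 | 93 |
| Unpooled z | 0.75 | 25 | 94 | 91 | 94 |
| Likelihood-ratio root | 2.6 | 38 | 96 | 94 | 94 |
| Log odds ratio z, 0.5 in every cell | about 0 | 0.1 | 10 | 27 | 86 |

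**4. Why 6% fails at 25 per arm.** The chance of no HCQ infection among 25 is 0.99^25 = 0.778. With none, the pooled z is 2.85 at 7 placebo infections and 3.09 at 8, so 8 are needed. P(8 or more of 25 at 10%) = 0.0023, and 0.0023 × 0.778 = 0.0018. A chance near 6% would require a stop at 5 v 0, since 0.098 × 0.778 = 7.6%, whereas stopping only from 6 v 0 gives 0.0334 × 0.778 = 2.6%. At 5 v 0 the z is 2.36 (pooled), 2.50 (unpooled), 2.74 (likelihood ratio) or 1.74 (log odds ratio with 0.5). All are below 2.9473.

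**5. A fixed 9-point gap, exact group-sequential power (%).**

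| Placebo v HCQ | Pooled z | Log odds ratio z, 0.5 added |
|---|---|---|
| 10 v 1 | 93 | 86 |
| 11 v 2 | 86 | 81 |
| 12 v 3 | 80 | 76 |
| 15 v 6 | 68 | 65 |
| 19 v 10 | 57 | 55 |

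With HCQ held at 1%, power rises with the gap: 97 and 95 at 12 v 1, and 99 and 99 at 15 v 1.

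**6. Zero cells.** At a 1% rate, the chance of no HCQ infection by the end is 0.99^100 = 37%. The unadjusted Wald log odds ratio is then undefined.

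**The case against.** The sentences before the 9-point wording fix the rates at 10% and 1%. When the Protocol varies the placebo rate, its figures reproduce with HCQ kept at 1%, and on that path the wording is true. The cases that fail need HCQ rates that neither document uses. This stands: the phrase is open to misreading but is not false in its own setting.

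The 6% is a correct evaluation of a standard approximation, and no decision rests on it. The printed boundaries govern stopping, and for the pooled z the exact type I error at 10% v 10% is 5.0%. That also stands, but the figure still misstates what the first look can deliver under every form of the statistic in the table.

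Both printed powers lie below the exact 93% and 86%, so they err on the cautious side. That is true for those two tests, but it does not reconcile 80% with 84%.

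A reader might infer that 84% is right and 80% a leftover. The documents do not support this. The drift that gives 84% power gives a 5.3% first-look stop, while the drift that gives 6.0% (2.79) gives 87.1% power. So 84% does not fit the stopping chances either.

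A reader might also take 2.6% as a ceiling for any test. It is not: an arcsine z is 3.28 at 5 v 0, crosses the boundary and gives about 7.6%. The plan does not name that statistic.

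**Conclusion.** The inconsistency is real: one design carries two powers in the Protocol, one of them is missing from the SAP, and the interim looks cannot account for the difference. The 6% first-look chance is wrong as a statement about 25 per arm. It is 0.2% for the pooled z, 0.75% unpooled, 2.6% for the likelihood ratio and about 0% for the log odds ratio z with 0.5 added. The 9-point wording needs its rates attached.

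Two stronger readings are not supported. The trial is not shown to be under-powered at 10% v 1%. Nor is the 27% shown to be wrong, since it runs from 0.1% to 38% with the choice of statistic.

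The results assume equal arms at each look and full evaluability. The 0.5 rule is my assumption. The planning method is not stated, so the origin of each printed figure is inferred.

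**What to change.** In both documents:

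- Name the form of the log odds ratio z (the score form, which equals the pooled z, or the Wald form) and the rule for a zero cell.
- State one power for that test, computed exactly with both looks and tied to 10% v 1%. This would be 93% for the pooled z, or 86% for the Wald form with 0.5 in every cell.
- Replace the 9-point wording with 10% v 1%, optionally adding power at 12% v 3% and 15% v 6%.
- Replace the 6% with the exact first-look chance for that test. Recompute the 27% and the 80% (and, in the Protocol, the 81%) the same way.

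This changes text only, with no change to sample size or boundaries. The cost is that some figures become less favourable: the first-look chance in every form tabulated, and the later stopping chances too if the Wald form is chosen.
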